**RATIONALE:**

tDCS studies typically report significant group effects despite the variability demonstrated among participants, with some showing clear, meaningful improvement, while others only show statistical improvement or none at all. These variable results may be related to the conventional stimulation intensity level of 2mA. Recent evidence suggests an electric field of at least one v/m is needed to affect local networks in the brain [15] reliably. However, tDCS at 2mA produces an electric field around only 0.6 v/m because a large amount of shunting (a dilution of the incoming current) occurs as the current travels from the electrode on the scalp, through the skin, skull, and cerebral spinal fluid (CSF), before reaching the brain. The most direct way to increase the electric field produced in the brain is to increase the intensity delivered. Current tDCS machines can have an intensity level of 4mA, resulting in more substantial electric fields than one v/m. We predict that if we were to administer tDCS at 4.0 mA, a more significant number of participants would show a meaningful response, and those who improve at 2mA may improve even more from 4.0mA due to having a larger electric field produced.

We aim to test this hypothesis in people with Alzheimer's Disease because they have unique attributes that may impact tDCS differently from other populations. More specifically, the amount

of shunting is predicted to be larger due to increasing CSF from brain atrophy [16]. Thus, 2mA may be too weak to be very effective in some people with Alzheimer's Disease due to the higher level of shunting. More significant improvements would be observed from a higher intensity level that can better interact with the remaining cortex. Alzheimer's Disease is also predominately female, and past studies have suggested men and women respond differently to tDCS [17-24]. For example, women have smaller skulls than men in general, which are predicted to receive more of the incoming stimulation. Finally, as Alzheimer's Disease is progressive, the degree of impairment may be relevant [25]. We will check if individuals who are more impaired benefit more when the stimulation intensity is set higher. The level of impairment will be measured in two ways: (1) the baseline score on a naming task (baseline severity); and (2) scores collected from cognitive testing (cognitive severity).

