## **Hypotheses Addressed**

The degree of improvement observed in people with Alzheimer's disease will be significantly greater when training is carried out at higher stimulation intensity (4mA vs. 2mA, SHAM).

There will be significantly more significant improvement observed when:

[figure not shown]
1. Individuals have more atrophy (decreased brain volume, higher CSF volume).
2. Individuals have a higher degree of impairment
3. The participant is female (possibly due to skull differences).

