In summary, training sessions have participants practice picture naming, as might occur in a typical speech therapy session for anomia, except the first 20 minutes are concurrent with tDCS, which is typical in tDCS studies. Most sessions will last around an hour. Due to the training involved, we expect participants will improve regardless of the stimulation condition but predict this improvement will be larger when done with real tDCS, and largest when done with 4mA tDCS. Related to this, we will check if this superiority of 4 mA over 2 mA is related to a participant's condition (e.g., sex, level of atrophy).

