### **Planned Analyses**

The primary outcome measure will be improvement on the naming lists administered, both a trained version and an untrained version. Improvement will be measured in terms of the number

of images correctly named post-training compared to baseline. A repeated-measures ANOVA will be run to compare the three stimulation conditions (SHAM, 2mA, 4mA) with sex (male, female) as a between-subject variable. This analysis will be conducted separately for the trained and untrained items. We expect to find the greatest improvement in the 4mA condition.

Next, we will calculate how much a participant improved in each condition by taking the naming score obtained at baseline for a naming list and subtracting it from the naming score obtained in the final stimulation session (e.g., 32 (final) – 20 (baseline) = an improvement score of 12). These scores are then used to produce tDCS effectiveness scores: the improvement score in the 4mA condition minus the improvement score in the SHAM condition; and the improvement score in the 2mA condition minus the improvement score in the SHAM condition. These tDCS effectiveness scores will then be the dependent variables in a multivariate logistic regression; once for trained items, one for untrained items. The predictors will be the CSF level of a participant, grey matter volumes and skull thickness around the IPL, impairment scores (baseline and cognitive severity), and interactive terms representing the sex of the participant. In this manner, we can examine what individual differences predict the tDCS response in people with AD, and if these predictors are the same for 2mA and 4mA tDCS, while checking for sex differences. We expect more significant levels of CSF, less IPL grey matter, thicker skulls, and greater impairment levels will be predictive of more substantial improvement in the 4mA condition because this stimulation intensity is needed to compensate for higher levels of shunting and severity. CSF and grey matter values may be less predictive for how well women respond to tDCS as their relatively smaller heads could compensate for increased shunting levels.

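### The predictor analysis names a logistic regression for outcomes that are signed numeric difference scores, with no cut-off or categories stated

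*Protocol*

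**What the plan says.** All of the operative text is in the Protocol, Planned Analyses. Improvement is the naming score at the final stimulation session minus the score at baseline. The section's example subtracts 20 from 32 to reach "an improvement score of 12". From this it forms two effectiveness scores. The first is "the improvement score in the 4mA condition minus the improvement score in the SHAM condition", and the second is the same difference for 2 mA. The next sentence reads: "These tDCS effectiveness scores will then be the dependent variables in a multivariate logistic regression". The regression is run once for trained and once for untrained items. Its predictors are CSF level, grey matter volume and skull thickness around the IPL, the two severity scores, and interaction terms for sex. Certain values of these predictors are expected to be "predictive of more substantial improvement in the 4mA condition".

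Three other places bear on what is meant:

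- The Rationale predicts that at 4 mA "a more significant number of participants would show a meaningful response".
- The Rationale also says: "We will check if individuals who are more impaired benefit more when the stimulation intensity is set higher".
- Training Sessions plans to examine whether "this superiority of 4 mA over 2 mA is related to" participant characteristics.

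**The concern.** A logistic regression models the probability of a category: yes or no in the binary form, ordered classes in the ordinal form. The outcome defined immediately before it is a number of images that can be negative, zero or positive. The Protocol contains no step that turns this number into a category.

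The regression carries weight. Hypotheses Addressed lists atrophy ("Individuals have more atrophy (decreased brain volume, higher CSF volume") and degree of impairment as conditions under which improvement should be larger. The repeated-measures ANOVA contains only stimulation condition and sex, so this regression is the only planned test of those two hypotheses. An analyst who follows the word *logistic* in its usual binary sense has to supply a cut-off. With two scores and two item lists, that could mean up to 2 × 2 = 4 cut-offs, all chosen after the data exist. The result would then depend on a rule the Protocol does not state, and the split would discard information.

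**Working it through.** **1. The type of outcome.** The Protocol's own example reproduces: 32 − 20 = 12. The effectiveness score is the difference of two such improvements. The length of the evaluated list is not stated. Assuming it equals the 45 images used in training (Training Sessions), improvement runs from −45 to +45 and effectiveness from −90 to +90. That is up to 2 × 90 + 1 = 181 whole-number values. The conclusion does not depend on the length of 45, because any list gives a signed count.

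**2. Whether the named model accepts it.** Signed whole-number scores were simulated for 54 participants.

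- A binary logit stopped, because its outcome must lie between 0 and 1.
- A binomial GLM returned meaningless coefficients of order 10^16.
- Linear regression fitted normally. With 11 predictors and an intercept it left 54 − 12 = 42 residual degrees of freedom. The 11 assume five main predictors, sex and five sex interactions.
- In a further simulated set with 15 distinct values, an ordinal logit did fit, with 14 thresholds.

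So only an ordinal logistic model could take the scores undivided, and the Protocol does not name one.

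**3. What the text points to.** The expectation attached to the regression concerns amount ("predictive of more substantial improvement in the 4mA condition"), and so does the impairment question in the Rationale. The prediction that more people will respond is a yes/no idea, but a meaningful response is never defined or tied to this regression. The comparison of 4 mA with 2 mA also suits undivided scores: (4 mA − sham) − (2 mA − sham) = 4 mA − 2 mA. In a linear model with the same predictors for both scores, the difference between a predictor's two coefficients is therefore its effect on the 4 mA advantage over 2 mA. Two split scores do not give this.

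**4. What a split would cost (illustration only).** Assume a normal score, small effects, and a split with proportion p on one side, none of which the Protocol states. The share of information kept is φ(z_p)² / [p(1 − p)], where φ is the standard normal density and z_p its p-quantile.

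| Split | Share kept | × 54 | × 60 |
|---|---|---|---|
| 50/50 | 0.637 | 34.4 | 38.2 |
| 30/70 | 0.576 | 31.1 | 34.5 |
| 20/80 | 0.490 | 26.5 | 29.4 |

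The 54 required and 60 recruited come from the Sample section, where they belong to the ANOVA. They serve here only as a scale.

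**The case against.** The strongest reply is that this is a one-word slip. The section speaks of how far each participant improved, gives a numeric example, and makes the scores themselves the dependent variables. An analyst holding those scores would meet the problem at once and fit a linear model. On that reading nothing is lost and the percentages above are hypothetical. Cut-offs and categories are also details that a protocol may leave to a statistical analysis plan, which is not at hand.

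Much of this stands. A slip is the likeliest explanation, and the information loss occurs only if the scores are split. The participant equivalents are rough: the Sample section lets people who cannot have an MRI continue, and they would lack the CSF, grey matter and skull predictors, so the number in the regression may be below 54.

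It does not remove the point. The Protocol is not silent on the model. It names one that does not fit the outcome it has just defined. A later plan could follow it only by inventing a cut-off or categories, or by choosing an ordinal model the Protocol never mentions; otherwise it must depart from the Protocol. The reference to a meaningful response gives a binary reading some support, so the text does not fully settle the matter.

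**Conclusion.** The concern holds: the named model does not match the outcome, and the Protocol contains nothing that would make it match. The effect is confined to the individual-differences regression, for trained and untrained items, and so to the atrophy and impairment hypotheses. The primary ANOVA and the sample size are untouched. The cost in information ranges from none, if *linear* was meant, to about 36% for a median split and 51% for a 20/80 split (1 − 0.637 and 1 − 0.490), assuming normal scores, small effects and a two-way split. The mismatch itself rests on none of these assumptions. It should be corrected before the analysis is run.

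**What to change.** In Planned Analyses, replace *logistic* with *linear*, so that the 4 mA and 2 mA effectiveness scores enter undivided as the two joint outcomes of a multivariate linear regression, run for trained and for untrained items as already planned. This changes wording only: same data, same participants, same predictors.

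If a responder or ordinal analysis is intended instead, state that model and define its cut-off or ordered categories before any data are seen. That also needs no new data, but a two-way split would give less precision from the same sample, as the table shows.

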## METHODS:

### Sample

Based on the previous study where tDCS was used for language training [6], we expect a partial eta square around 0.20. For 80% power to detect a difference across the three levels of intensity, while also accounting for the sex of a participant, a repeated-measures ANOVA test at an alpha level of 5% will require 54 participants with AD (27 men and 27 women). To compensate for anticipated attrition over the study, we will recruit a sample of 30 men and 30 women, 60 total.

These participants would have received the diagnosis of probable AD from Baycrest's Memory Clinic expert staff [29, 30] according to standard clinical criteria. Only patients with no family history of epilepsy and who can give consent will be tested. We will seek people with mild to

moderate AD (Reisberg stages 3, 4, or 5, [34]) who score between 18 and 25 on the MoCA [26]. Participants must show no history of stroke or traumatic brain injury, nor shunts or metal in the head that could interfere with the delivery of tDCS. Finally, people will have no evidence of significant heart disease, alcoholism, drug use. All enrolled participants will be expected to complete an MRI; however, if they are unable to complete an MRI due to the presence of an exclusion criterion, they will still be allowed to complete all subsequent stages of the study. Participants will be evaluated and trained using different naming lists each round. We have developed equivalent versions of these naming lists in our lab, which allows us to use a different trained and untrained list each round.

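### The plan promises to compare predictors between 4 mA and 2 mA, but names no test of that difference; the contrast can be had from its two SHAM-referenced scores and should be stated

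*Protocol*

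**What the plan says.** The protocol states the 4 mA versus 2 mA question in two places.

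- Training Sessions, closing summary: "we will check if this superiority of 4 mA over 2 mA is related to" the participant's condition, with sex and atrophy as the examples.
- Planned Analyses: the moderator regression is said to let the investigators examine "if these predictors are the same for 2mA and 4mA tDCS, while checking for sex differences".

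Planned Analyses also expects more CSF, less grey matter, thicker skulls and greater impairment to go with larger gains at 4 mA, because "this stimulation intensity is needed to compensate for higher levels of shunting and severity".

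The analysis meant to answer this uses two scores per participant. For the higher intensity the score is "the improvement score in the 4mA condition minus the improvement score in the SHAM condition". The lower intensity has a score built in the same way and again set against SHAM, namely "the improvement score in the 2mA condition minus the improvement score in the SHAM condition". On the model it says: "These tDCS effectiveness scores will then be the dependent variables in a multivariate logistic regression; once for trained items, one for untrained items". On the predictors: "The predictors will be the CSF level of a participant, grey matter volumes and skull thickness around the IPL", followed by the two impairment scores and interaction terms with sex. No 4 mA-minus-2 mA score is defined, and no comparison of coefficients between the two scores is named.

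**The concern.** Whether a predictor acts differently at 4 mA than at 2 mA is a question about a difference of slopes. A slope on either SHAM-referenced score does not test it. A predictor that acts equally at both intensities gives a positive slope on 4 mA minus SHAM just as one specific to 4 mA does. That slope alone therefore cannot show that the higher intensity is needed.

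The plan presents its described analysis as answering the comparison, yet leaves out the step that would do so. Without it, the natural shortcut is to list which predictors reach significance for each score. That can make equal predictors look different. It can also hide a real difference when both scores are significant. At stake is the plan's conclusion about who gains from the higher intensity.

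**Working it through.** **1. Is the contrast contained in the two scores?** Write y4, y2 and y0 for a participant's improvement at 4 mA, 2 mA and SHAM. Then (y4 − y0) − (y2 − y0) = y4 − y2, so SHAM cancels. Least squares is linear in the outcome, so with the same predictors and the same participants

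b(4−SHAM) − b(2−SHAM) = b(4−2).

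A numerical check on one simulated data set gave the same t both ways: 0.2573 from the equality-of-coefficients contrast in the joint model and 0.2573 from the regression of 4 minus 2, each on 42 df.

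**2. Why one slope is not enough.** Take true slopes of 0.4 at 4 mA, 0.4 at 2 mA and 0 at SHAM. Then b(4−SHAM) = 0.4 and b(2−SHAM) = 0.4, but b(4−2) = 0. The first slope is positive although the predictor does not separate the intensities.

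**3. What would comparing significance do?** The protocol gives no figure for this analysis, so there is none to reproduce.

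- From the protocol: n = 54 (Sample); five predictors (CSF, grey matter, skull thickness, two impairment scores) with sex interactions (Planned Analyses).
- Assumed: linear regression, because the scores are numeric differences; SD 1 per condition; SHAM slope 0; independent standardised predictors; sex included as a main effect and effect-coded; two-sided 5% tests; correlation between conditions of 0, 0.5, 0.7 or 0.8.
- Residual df = 54 − (1 intercept + 5 predictors + 1 sex + 5 interactions) = 54 − 12 = 42.

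Simulated with 8,000 to 10,000 runs per case:

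| Case | r = 0 | 0.5 | 0.7 | 0.8 |
|---|---|---|---|---|
| Equal slopes 0.2: exactly one score significant | 18% | 25% | 31% | 33% |
| Equal slopes 0.4: exactly one score significant | 32% | 28% | 14% | 5% |
| Equal slopes 0.6: exactly one score significant | 25% | 7% | 1% | 0.1% |
| Slopes 0.4 (2 mA) and 0.8 (4 mA): both scores significant | 42% | 71% | 89% | 97% |
| Same slopes: power of direct 4-versus-2 test | 43% | 70% | 89% | 97% |

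Under equal slopes the direct test rejects in about 5% of trials throughout. A fresh run of 6,000 trials per case agreed with every row to within about one percentage point.

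**4. Sensitivity.** With sex dummy-coded, so that the slope refers to one sex, the equal-slope 0.4 row becomes 26 / 33 / 29 / 22% and the power row 26 / 45 / 64 / 80%. Participants who cannot have an MRI stay in the trial ("they will still be allowed to complete all subsequent stages of the study", Sample) but lack three of the five predictors. If 45 had complete data (assumed), effect-coded power would be 35 / 60 / 80 / 92% and the equal-slope 0.4 row 31 / 31 / 21 / 10%.

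**5. Multiplicity of the added tests.** If the tests were independent, five give 1 − 0.95^5 = 23% and all 11 coefficients give 1 − 0.95^11 = 43%. In the simulated model, where tests share a residual variance, the chance of at least one false positive per list is about 22% for five and about 40% for 11.

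**The case against.** The strongest reply is that the plan makes both scores the dependent variables of one multivariate regression per naming list. Read literally, this is a joint model, and step 1 shows that it holds exactly the contrast needed. Naming a post-estimation contrast is detail that a statistical analysis plan often supplies, and that document is not at hand. This stands in part: the choice of outcomes is not wrong. But Planned Analyses goes beyond silence, because it says that the analysis as described will answer the 4-versus-2 question. The word multivariate may also have been meant as multivariable, with one model per score, and the text does not settle this.

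Second, no passage says predictors will be compared by significance. That is correct. The percentages describe a shortcut the plan leaves open, not one it prescribes.

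Third, the inputs are assumed and the error rate can be made small or large by choosing them. Also correct, which is why a range is given.

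Fourth, the formal moderator hypotheses under Hypotheses Addressed predict larger improvement with atrophy, impairment or female sex, not a difference between intensities. The ANOVA's condition-by-sex interaction also already includes a 4-versus-2 component for sex. Both points limit the reach of the concern. The two promises quoted above remain, and the interaction test over three conditions does not isolate 4 mA versus 2 mA.

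**Conclusion.** The concern holds as an unstated contrast. The protocol twice promises a comparison of 4 mA with 2 mA across participant characteristics, fixes two SHAM-referenced scores, and names no test of the difference between them.

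A reader might infer that referencing both scores to SHAM makes the comparison impossible. It does not: in a linear model the contrast is an exact by-product of the two scores. A reader might also infer that the investigators will misread patterns of significance. The documents do not say so.

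Should predictors be compared that way, truly equal slopes would look different in under 1% to about 33% of trials, against about 5% for the direct test. Where that rate is low because slopes are large or conditions highly correlated, the opposite error takes over: for slopes of 0.4 and 0.8, both scores are significant in 42% to 97% of trials. These figures rest on the assumed slopes, SDs, correlations and coding, and on a linear model. That a logistic model does not suit numeric difference scores is a separate matter and carries no weight here. This is a secondary analysis, but who gains from the higher intensity is a stated aim, so the correction is worthwhile.

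**What to change.** In Planned Analyses, keep the two SHAM-referenced scores and add for each naming list:

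- the 4 mA-minus-2 mA improvement difference as a dependent variable in a linear regression with the same predictors, or the equivalent equality-of-coefficients test in the joint model;
- the 4-versus-2-by-sex contrast, following the condition-by-sex interaction in the ANOVA.

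Base any statement that predictors differ between intensities on these estimates, each with its 95% confidence interval. State that a non-significant difference will not be read as showing that predictors are the same. Say which coefficients will be tested, and label the tests exploratory or adjust them for multiplicity.

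The cost is one regression or contrast per list, plus the sex contrast, on data already collected. The downsides are the false-positive risk in step 5 and limited power: 43% to 70% at correlations of 0 to 0.5 for a slope that doubles from 0.4 to 0.8, and less with dummy coding or missing MRI values.

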## **Funding**

This study is supported by the Alzheimer's Society, which reviewed the submitted protocol, and awarded funds to [name] [name] towards completing the proposed study.

